 - Higher levels of reassurance of the benign nature of MSKP.
 - More adaptive MSKP coping and psychological flexibility.
 - Higher self-reported levels of physical activity.
 - More positive global ratings of change.
 - Lower number of healthcare visits, referrals for diagnostic imaging and to specialist/tertiary care for MSKP, lower analgesic medication use, fewer sick leave days and lower direct costs.
 - More positive and concordant patient and physiotherapist evaluations of MSKP-related shared understanding, communication, participation, involvement and emotional support at the initial physiotherapy consultation.
2. Improvements in MSKP illness perceptions and higher levels of reassurance of the benign nature of MSKP mediate improved pain intensity and pain self-efficacy as a result of exposure to the PainSMART-strategy compared to usual physiotherapy management alone.

Null hypothesis (H0): no statistically significant or clinically relevant differences between the intervention group (PainSMART-strategy as an adjunct to usual physiotherapy management) and the control group (usual physiotherapy management alone).

Exploratory research questions:

1. What baseline factors are predictive of improved patient outcomes after exposure to the PainSMART-strategy?
2. What baseline factors are predictive of the persistence of MSKP?
3. What type of psychological factors and strategies are associated with patient outcomes after exposure to the PainSMART-strategy?

4. Is pain self-efficacy a potential mediator of the PainSMART-strategy's effect on health outcomes?
5. What are patients and physiotherapists experiences of the PainSMART-strategy?

Primary research question for the qualitative phase of the research program:

- Does exposure to the PainSMART-strategy influence communication around pain at the initial physiotherapy consultation?

Dimensions to explore via the qualitative phase of the research program:

- Describe how physiotherapist and patient participants incorporate the PainSMART-strategy into the initial physiotherapy consultation.
- Explore potential explanations for the quantitative results of the randomized controlled trial (RCT).
- Describe the participating patients' understanding of MSKP and explore how this may relate to the PainSMART-strategy's theoretical underpinnings.
- Explore if patients' understanding of MSKP diverge from the understanding of the physiotherapist during the initial consultation.

Methods

Trial design

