The PainSMART-project is a research program with a collective suite of studies utilising mixed methods, centred on a randomised controlled, superiority trial with two parallel groups. A 1:1 group allocation ratio will be applied. The control group and statistician will be blinded. One independent statistician will be blinded for the primary analyses. Another independent statistician will be responsible for database development and linking of patient and physiotherapist data. The results of the RCT will be reported according to the Consolidated Standards of Reporting Trials (CONSORT) statement and the CONSORT patient-reported outcomes checklist (Calvert et al., 2013; Schulz et al., 2010). The final phase of the RCT will include qualitative data collection which will be reported in line with the Consolidated Criteria for Reporting of Qualitative research (COREQ; Tong et al., 2007).

Study setting

This study is a multi-centre RCT that will be conducted at five primary care physiotherapy departments within the Swedish regions of Östergötland (RÖ) and Jönköping (RJL). All four physiotherapy departments within RÖ and one physiotherapy department within RJL have agreed to participate. Collectively these centres employ around 130 physiotherapists and provide initial consultations to approximately 30 000 unique individuals in a one-year period. A list of the participating physiotherapy departments is available from the corresponding author on request.

Eligibility criteria

Potentially eligible patient participants are all adults (18 years or older) seeking primary care for MSKP who are triaged and booked for an initial physiotherapy consultation at one of the participating physiotherapy departments. Inclusion and exclusion criteria are shown in Table 1. A flow chart of the patient participants' path through the study is shown in Figure 1. All physiotherapists who provide care to patients booked for a consultation for MSKP at one of the participating physiotherapy departments are eligible to participate.

Table 1. Randomised controlled trial inclusion & exclusion criteria

Inclusion criteria

 Patients who, via telephone or online text-based triage, are judged to have benign MSKP and are booked for an initial physiotherapy consultation Adult patients (18 years or older)
Exclusion criteria

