The film shows a dialog between a physician and a patient with MSKP. The film is seven minutes long and divided into three sections. Section one (4 minutes 30 secs) presents the idea that MSKP is a complex and necessary biopsychosocial protective system that does not accurately reflect the anatomical state of the body (Moseley & Butler, 2017). Section one also provides reassurance that MSKP is very rarely caused by serious pathology (Finucane et al. 2020). Section two (1 minute 30 secs) provides advice on active coping strategies, such as encouraging exercise and work despite some pain, in an attempt to reconceptualise the commonly held belief that a painful body part needs to be rested (Caneiro et al., 2020; Setchell et al., 2017). Section three (50 secs) aims to prepare patients for their initial physiotherapy consultation by encouraging them to reflect on the time when their MSKP first developed and their overall life situation with the aim of facilitating a more biopsychosocial consultation. Following the film the patients will rate eight statements that summarise the film's key-messages as listed in Table 2.

The film aims to target patients' impeding MSKP illness perceptions, improve pain self-efficacy and encourage adaptive self-management strategies, all factors that are hypothesised to improve pain intensity over time. This requires the content of the film to improve factors such as maladaptive perceptions of the causes of MSKP and its persistence (for example, low outcome expectation, anxiety, catastrophizing, and fear avoidance beliefs) and low pain self-efficacy. The content of the film addresses all the dimensions of the CSM and this is outlined in Table 2 (Leventhal et al., 2016).

Stage two: The consulting physiotherapist will, via four structured questions, initiate a discussion about the film's contents and the questionnaires the patient has completed prior to the initial consultation. The four questions ask the patient if any of the content within the questionnaires they have completed have generated any thoughts or reflections, whether they had actually seen the film, whether the film generated any thoughts or reflections and if there was anything in particular they took from the film. It is hoped that these questions, in addition to the film providing a shared basis for patient-centred MSKP communication, will facilitate a higher value initial consultation (Epstein et al., 2005; Lehman, 2017).

Who

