on generalisability (Mercieca-Bebber et al., 2018). All outcome data will be compared based on the ITT principle. This means that all patients that have been randomised remain in the analysis based on their group allocation. In the event of substantial missing data, evaluation of the mechanisms for missing data will be used (Enders, 2011). Missing data will otherwise be handled under the missing at random assumption (Enders, 2011). Multiple Imputation or Maximum Likelihood estimation will be used assuming that missing data is conditional on variables included in the model. Imputation method considering missing at random or not missing at random will be used in the ITT analysis. Patients who cancel their initial physiotherapy consultation will be excluded from the PREM analysis but will remain in the study for PROM and healthcare register data analyses.

Study monitoring and harms

There will be no data monitoring committee since the study is independent from the sponsor and the intervention is implemented as an adjunct to usual physiotherapy management with low risk for unexpected adverse events. The PROMs included in the study are sensitive to worsening in the patients' condition. An internal pilot interim analysis was planned and conducted (February 29th, 2024) after approximately 50% of the initially planned sample (n = 229) had consented to the study and reported outcomes at time point two (72-24 hours prior to the initial physiotherapy consultation) and three (24 hours post the initial physiotherapy consultation). This interim analysis enabled evaluation of the viability of the a-priori sample size calculation and the recruitment frequency. The analysis utilised linear mixed models to investigate between group differences (effect size) for change from baseline to time points two and three for outcome. The significance level for the interim analysis was p=0.05. After interim sample size calculation, the sample size was adjusted slightly to take loss to follow-up into account. The sample size calculation is described under the protocol heading sample size. The trial would have been stopped if the internal pilot interim analysis could not be performed due to not attaining 50% of the sample size at Time point two and three within six months. No further interim analyses are planned.

Ancillary and post-trial care

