The analysis populations include an intention-to-treat population (ITT) and a per-protocol population for this trial. The ITT population will include all randomised patients according to the treatment they were randomised to receive. ITT is the primary efficacy analysis population for this study. A per-protocol population will be considered for participants who received the intervention protocol with no or minor deviation from the protocol.

[Trial Population](#)

[Screening data](#)

The total number of eligible participants could not be collected during the study as it was considered too resource intensive and would not be sufficiently reliable. Register data on numbers of first physiotherapy consultations for MSKP at the rehabilitation units during the study recruitment period will be collected. Demographic and baseline characteristics (see "Demography and baseline characteristics") will be collected to enable analysis of the representativeness of the study sample (patient participants).

The following demographic data will be collected and presented to enable analysis of the representativeness of the sample of participating physiotherapists: employer, age, sex, level of education, number of years working as a physiotherapist.

Eligibility

The inclusion and exclusion criteria are reported in the protocol. In the case that participants have initially fulfilled these criteria and been randomly allocated to a group but at a later time point have been found to not fulfil the criteria (e.g. the late diagnosis of a serious medical condition), the number of ineligible patients randomised, if any, will then be reported with reasons for ineligibility.

Recruitment

A CONSORT flow diagram will be used to summarize the number of patients who were:

- Eligible for screening
- Ineligible at screening
- Eligible at screening but not randomised - Declined to participate (n=....)
- Randomised (n=...)
- Number excluded post randomisation (n=...) *Reasons ex. consent withdrawal, late diagnosed serious pathology
- Allocated to intervention (n=...)
 - Received allocated intervention (n=...)
 - No exposure to the film and the PainSMART-questions (major deviation) (n=...)
 - No exposure to the PainSMART-questions (minor deviation) (n=...)*
 - *Reason: Physiotherapist adherence to protocol (n=...); Cancelled physiotherapy consultation (n=...)
 - Exposure to the whole PainSMART-strategy (n=....)
 - Did not receive allocated intervention, plus reasons (n=...)

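### The SAP's flow diagram names late-diagnosed serious pathology as a reason for exclusion after randomisation, which conflicts with the plan's own ITT definition

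*SAP*

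**What the plan says.** **Analysis population.** The SAP (Statistical analysis population) states: "The ITT population will include all randomised patients according to the treatment they were randomised to receive". It adds: "ITT is the primary efficacy analysis population for this study". The protocol (Missing data) explains ITT in the same sense: "This means that all patients that have been randomised remain in the analysis based on their group allocation". The only other population defined is per-protocol. It depends on exposure to the film and to the physiotherapist's questions, not on diagnosis.

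**Exclusion line.** The flow-diagram template in the SAP (Recruitment) contains "Number excluded post randomisation (n=...) *Reasons ex. consent withdrawal, late diagnosed serious pathology". It stands above the lines that split patients by arm. SAP Participant drop-out also foresees reporting exclusions from analysis, with reasons, at each stage.

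**Eligibility.** The SAP (Eligibility) considers patients who met the criteria at first, were allocated, and were later found not to meet them. Its example is a serious condition diagnosed late. It commits to reporting their number and the reasons. It does not say that they leave the analysis.

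**Entry criteria.** Protocol Table 1 admits patients who, at triage, "are judged to have benign MSKP and are booked for an initial physiotherapy consultation". The matching exclusion criterion is also a judgement, about suspected red flags.

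**Intervention and hypotheses.** Of the film, the protocol says: "Section one also provides reassurance that MSKP is very rarely caused by serious pathology". Among the hypothesised benefits is: "Lower number of healthcare visits, referrals for diagnostic imaging and to specialist/tertiary care for MSKP".

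**The concern.** A patient judged benign at triage and diagnosed later was correctly enrolled, so the diagnosis is something that happened after randomisation. Excluding on such an event is safe only if it is unrelated to allocation, and here that cannot be assumed. The strategy is meant to change how worried patients are and how often they are imaged or referred, and those are plausible routes to a serious diagnosis. The treating physiotherapists know the allocation and the coordinators are not blinded. Neither document gives a rule for who decides such an exclusion, or whether that person is blinded.

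Three things are at stake. The primary population could be read in two ways. Dropped patients would take their visits and referrals out of the register outcomes, where fewer counts as better. And late diagnoses could appear in the report only as one pooled number, because the template does not place them by arm. Protocol Study monitoring and harms provides no data monitoring committee and names only worsening on the PROMs, which do not record a diagnosis.

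**Working it through.** **1. Text against text.** No figure in the plan is at issue, so there is none to reproduce.

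| Place | What happens to a late-diagnosed patient |
|---|---|
| SAP, Statistical analysis population | Stays in, by allocated arm |
| Protocol, Missing data | Stays in, by allocated arm |
| SAP, Eligibility | Counted with reasons; analysis not mentioned |
| SAP, Recruitment (flow template) | Example of a patient excluded after randomisation |

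The fourth row cannot be squared with the first two. The template pairs late pathology with consent withdrawal, which SAP Participant drop-out classifies as the end of all follow-up and data collection. An analyst could fairly read both as removal. No defined population matches that reading: there is no modified ITT set, and a late diagnosis is not among the listed protocol deviations.

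**2. Direction of any bias.** Suppose these patients report worse pain and have more referrals than the rest (an assumption). If the film lowered detection, the control arm would lose more of them and would look better for it. If better-prepared consultations raised detection, the reverse would follow. The direction cannot be fixed in advance.

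**3. Scale.** Inputs:
- 450 patients at baseline (protocol, Sample size), about 225 per arm at 1:1.
- Rate p of late-diagnosed serious pathology: not in the documents. Assumed range 0.2% to 2%.
- Number dropped from one arm, k = 1 to 5, each with a pain change D = 2 to 4 NRS points worse than the rest: assumed.

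Formulas:
- Expected cases per arm = 225p.
- Chance of at least one case in the trial = 1 − (1 − p)^450.
- Power to show a doubling (p against 2p, one-sided 0.05) = Φ[(p − 1.645·SE0)/SE1], where SE0 = √(2·1.5p(1 − 1.5p)/225) and SE1 = √([p(1 − p) + 2p(1 − 2p)]/225). This normal approximation is rough at such small counts.

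| Assumed p | Expected per arm | Chance of at least one in 450 | Power for a doubling |
|---|---|---|---|
| 0.2% | 0.45 | 59% | 10% |
| 0.5% | 1.1 | 90% | 15% |
| 1% | 2.3 | 99% | 22% |
| 2% | 4.5 | about 100% | 34% |

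With the full 490 patients (245 per arm), the expected number per arm is 0.49 to 4.9 and the chance of at least one is 63% to about 100%.

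Shift in one arm's mean pain change = kD/225:
- smallest: 1 × 2/225 = 0.009 points
- largest: 5 × 4/225 = 0.089 points

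The sample size section uses a difference of 2 points, so the largest shift is 0.089/2, or about 4% of it.

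If each dropped patient had one imaging referral more than the rest, mean referrals per patient in that arm shift by k/225, from 1/225 = 0.004 to 5/225 = 0.022.

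**The case against.** The strongest reply is that the SAP does not plan this exclusion. The line is an example in a blank reporting template. The Eligibility paragraph only promises a count, the ITT definition has no exception, and the primary analysis section follows ITT without an exclusion rule. This stands in part: the text permits the exclusion but does not order it. It does not remove the ambiguity, because a SAP should not allow two readings of its primary population.

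A reader might also infer that missed diagnoses would be hidden among the exclusions. The documents do not support that. A patient must be diagnosed to be excluded, so an undiagnosed patient stays in the ITT set with all data.

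Nor do they support calling this the one harm of the film, or saying that a planned safety comparison is lost. No comparison of late diagnoses is planned, and a lower detection rate is only a possibility. Patients in both arms are screened for red flags at triage, are booked to see a physiotherapist, and have unrestricted access to other care (protocol, Concomitant care; Ancillary and post-trial care). Imaging and tertiary-care referrals are compared between arms.

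Finally, the rates are assumed, and the protocol's only statement on frequency is that serious causes are very rare. That stands, and it is why the numbers above only illustrate scale.

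**Conclusion.** The inconsistency is real and should be settled before analysis. As written, correctly enrolled patients may be excluded on a post-randomisation event whose detection could depend on arm, against the ITT rule in both documents.

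It is not a material threat to the primary estimate: the shift in an arm's mean pain change is at most about 0.09 NRS points in the cases tried, under assumed numbers and assumed differences in pain change. The gain from correcting it is one unambiguous primary population, register outcomes that keep these patients' visits and referrals, and a count of late diagnoses that can be read by arm. That count would be descriptive. With 10% to 34% power for a doubling, it could not serve as a test, and similar counts in the two arms would not show that the strategy is safe in this respect.

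**What to change.** 1. In SAP Recruitment, delete late-diagnosed serious pathology as an example reason for exclusion after randomisation.
2. In SAP Eligibility, state that patients who met the criteria at triage and are diagnosed later stay in the ITT set in their allocated arm, for the PROM and the register outcomes.
3. Report the number of such patients, with reasons, by arm, next to the imaging and specialist-referral results, and label it descriptive. Say how the cases came to light, since the documents describe no systematic way of finding them.
4. If wanted, add an analysis without these patients as a sensitivity analysis.

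The cost is mainly SAP wording, because the count and reasons are already required. Time from baseline to diagnosis should be given only where it is already known: the documents do not list it as collected, and requiring it would be a new data item. The downside is that a few patients whose pain is not benign stay in the primary set.
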